3.2.3 Exploratory Outcome Measures

Secondary Objective Measures: Longitudinal tracking of vaccine-induced B cell responses with special emphasis on broadly neutralizing HA stem reactive responses by:

- Determination of the dominant antibody families (clonotypes) induced by influenza vaccination.
 - Use single cell sorting and multiplex PCR to identify influenza specific clonotypes among the blood plasmablasts at day 7 post-vaccination.
 - Use proteomics-directed cloning to examine the dominant influenza specific clonotypes present in the serum prior to vaccination and at 14, 28, 90, and 365 days post-vaccination.
 - Use deep sequencing to track the frequency of each clonotype in the bone marrow plasma cell compartment at days 0, 28, and 365 post-vaccination and in the memory B-cell compartment at days 14, 28, 90, and 365 post-vaccination.
 - Identify which clones persist to day 365 post vaccination and examine whether the same plasmablast clones are re-amplified after each vaccination.
 - Identify consensus antibody sequences within the memory B-cell and long lived plasma cell compartments at day 28 and day 365 post vaccination for each clonotype.
 - Examine whether specific antibody features (hypermutation levels, antigen binding affinity, cross reactivity to previous vaccine strains) are associated with each compartment.
 - Examine whether these antibody features are correlated with the persistence of a given antibody family out to day 365.

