4 STUDY DESIGN

Longitudinal assessment of the participants will be made at every study visit. Assessments will be performed at day 0, 7, 14, 28, 90 and 365 days after immunization as outlined in the following table. Participants will be screened for the presence of both expected reactions to vaccination and for unexpected adverse reactions and enrollment will take place within two weeks post-screening. Subject enrollment will commence with the availability of the seasonal flu vaccine and last for up to 365 days. See table in appendix A. Subjects will be offered the opportunity to participate in the study for up to 3 consecutive years provided eligibility criteria are met each year. Subjects who elect to continue in the study after the first year of participation will be rescreened to verify continued eligibility and re-consented prior to subsequent participation. Re-enrolling subjects will receive new subject identifiers and will count towards the total enrollment number for subsequent years of participation. Enrollment for the next year will begin with the availability of the seasonal flu vaccine. For subjects who elect to re-enroll in the study, the Day 365 visit (\pm 3 month window) would also be the Day 0 visit for the subsequent year.

Due to the COVID-19 pandemic, all non-essential research was halted in mid-March 2020. New enrollments were placed on hold for this study. Follow-up visits were also halted, which impacted the timing of participants' subsequent follow-up visits. For this study, there are participants whose Day 28 and Day 90 visits were impacted. We will request an expansion of the study window for the participants whose visits were impacted. Additional details regarding this are detailed further in the protocol. None of the other visits were impacted.

Dependent upon Emory's guidelines in response to the evolving nature of the pandemic and the prioritization of studies being allowed to re-open, time will be needed to secure the appropriate approvals and clearance to bring research participants back for their missed visits. As such, we would like to request that the missed visit windows for the Day 28 and Day 90 visits be extended for a maximum of up to 180 days, to ensure that ample time is available to bring participants back for their missed visits.

Enrollment for this study ended on March 31, 2020.

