- **Day 28 post vaccination study visit (+/- 2 days):** Subjects will have clinical safety labs drawn including a platelet count and hemoglobin and hematocrit (4ml of blood) Females of childbearing potential will have a urine pregnancy test performed, and the test result must be negative for the subject to continue with study participation. The results of the blood tests must be assessed by the study physician as within a healthy range for continued study participation using the most current normal lab ranges, and evaluated for clinical significance of lab values that fall outside of normal range. Subjects will have 64 ml of blood drawn for antibody testing. Vital signs including oral temperature, blood pressure, pulse rate and respiratory rate will be obtained. A health assessment will be performed including an inquiry about any illness or health change since the last study visit. Concomitant medications will be reviewed and updated. An assessment will be made for any adverse events or serious adverse events. Participants will receive a physical exam by a licensed to make medical diagnoses and listed on the Investigator of Record Form as the site principal investigator or sub-investigator. The Adverse Event Report Form will be updated if indicated. Study eligibility criteria will be reviewed by the study nurse and physician and confirmed that the subject meets all inclusion and none of the exclusion eligibility criteria prior to the bone marrow aspirate procedure. [name] as site principal investigator or the sub-investigator will explain the bone marrow aspirate procedure, and the informed consent document for the procedure will be signed by the subject in the presence of [name]. The bone marrow aspirate procedure and aspirate volume will be the same as the same as at study enrollment.
 - Due to the COVID-19 pandemic, all non-essential research was halted in mid-March 2020.
 - One participant had their Day 28 visit halted.
 - We are requesting that the Day 28 window be extended by a maximum of up to 180 days, to allow completion of the follow-up visit for the impacted participant.
 - The participant will be contacted by phone or via encrypted email message to arrange scheduling of subsequent visits.
 - To assist with assessing symptoms, the COVID-19 Screening Questionnaire/Script will be reviewed with participants prior to bringing the participant in for follow-up visits.

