marrow will be tracked by ELISPOT, which provides a quantitative measurement of ASC numbers in which each cell creates a spot on a plate based on the adherence of the antibodies which it produces to a capture antigen. Peripheral blood mononuclear cells or bone marrow mononuclear cells will be isolated using CPT tubes or histopaque purification, respectively. cells will be seeded into ELISPOT wells coated with reagents for capturing total IgG, IgM, or IgA (to measure total ASC numbers), or coated with the influenza vaccine (to measure total vaccine-specific responses), or coated with the head or stem domains of the influenza HA antigen (to measure the specific HA domains targeted by the response). To measure antigen-specific bone marrow plasma cell responses, which are low in frequency, ASCs will be enriched using magnetic bead separation prior to coating in ELISPOT plates.

- Clonotypic analysis of influenza specific memory B-cells and plasma cells in the blood and bone marrow of vaccinated subjects. Responding ASCs present in the blood at day 7 post vaccination will be sorted by flow cytometry and seeded into PCR plates for amplification of Ig heavy and light chain genes. Related antibody rearrangements present in multiple wells will be cloned and expressed as recombinant proteins to determine their reactivity towards influenza. The frequency of these clones in the bone marrow ASC compartment as well as the blood ASC and memory B-cell compartments will be determined using bulk RNA isolated from sorted bone marrow plasma cells. We determine the frequency of each clone over time in this bulk RNA using both Next Generation Sequencing (NGS) analysis and quantitative PCR using clonotype-specific primers and Taqman fluorescent probes.
- Defining the antibody-intrinsic features that promote long-term persistence of bone marrow plasma cells and memory B-cells. The sequences of vaccine-specific clonotypes in the bone marrow at early and late time points following vaccination will be determined from the NGS data. We will analyze these sequences for their level of somatic hypermutation, using tools available on the International Immunogenetics information system (IMGT) website. We will determine the impact of these mutations on affinity for antigen by expressing mutated or unmutated versions of the parental clone as recombinant proteins followed by ELISA and Biacore assays.

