11.2 Sample Size Considerations

A major goal our study is to understand the longevity of plasma cell responses directed against different determinants in the influenza vaccine. Our preliminary data has suggested that plasma cell clonal responses against conserved epitopes may be smaller in number and less prone to persist compared to responses against epitopes which are unique to the particular hemagglutinin strains used in the current year's vaccine. Our deep sequencing data suggests that after one year the frequency of the average vaccine-induced clone in the bone marrow is approximately 33% of the frequency observed at one month. However, there is a large variability in this maintenance (standard deviation of 44%). The small number of cross-reactive clones we have tracked so far have been undetectable after one year, suggesting that their maintenance is substantially lower than the average clone. We wish to be 80% confident in being able to detect whether the maintenance of these cross-reactive clones is at least 3-fold lower than for the average clone (i.e. 11% maintenance vs. 33%) with a P-value less than 0.05. This will require the longitudinal tracking of at least 25 broadly cross reactive plasma cell clones in our patient cohort. Our initial data suggests that we should be able to identify a single broadly cross-reactive clonotype in approximately 50% of our donors, meaning that a sample size of 50 donors will be required to follow 25 cross-reactive clonotypes. With our planned sample size of 55 donors, this allows for a potential dropout rate of 10%.

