11.4 Final Analysis Plan

We will use the unpaired Student's t-test to compare the frequencies of strain-specific and broadly cross-reactive clonotypes in the marrow after one year as expressed as a percentage of their frequencies at one month post vaccination. We will also work to develop a multi-phase exponential decay model for plasma cell persistence in the blood and bone marrow over time. We will use ANOVA to evaluate the contributions of antibody specificity (head vs. stem specific; broadly reactive versus strain specific reactivity), affinity for antigen, and level of hypermutation on the observed exponential decay constants of individual clones in each decline phase that we identify through our modeling. This work will be performed in collaboration with the Emory/UGA CEIRS Data Management Team headed by [name] using the approved Data Management Plan for this contract.

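### Does the one-year clone-maintenance t-test need a new rule for clones that are undetectable at Day 365?

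*Combined protocol and SAP*

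**What the plan says.** Section 11.4 (Final Analysis Plan) names an unpaired Student's t-test of strain-specific against broadly cross-reactive clonotypes. The variable is one-year marrow frequency "as expressed as a percentage of their frequencies at one month post vaccination". No scoring rule is given for a clone seen at one month and not at one year.

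Section 11.2 (Sample Size Considerations) shows that such clones will occur: "The small number of cross-reactive clones we have tracked so far have been undetectable after one year", which the plan reads as "suggesting that their maintenance is substantially lower than the average clone". The same section sizes the study on 11% versus 33% maintenance with a standard deviation of 44%, and takes the 33% from the group's deep sequencing data.

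On measurement, Section 8.2 says: "We determine the frequency of each clone over time in this bulk RNA using both Next Generation Sequencing (NGS) analysis and quantitative PCR". Section 3.2.3, which lists clonotype tracking as exploratory, is more specific: "Use deep sequencing to track the frequency of each clonotype in the bone marrow plasma cell compartment at days 0, 28, and 365 post-vaccination". No detection limit is stated in either place.

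**The concern.** For a clone not found at Day 365, the ratio is known only to lie between 0 and the detection limit divided by the Day 28 frequency. An analyst could score it 0, score it at that upper bound, or drop it. The preliminary data suggest that many cross-reactive clones will be in this position, and this comparison is the only one used to size the study. If the choice were made after seeing the data, it could decide the result.

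There is also a possible bias. Section 11.2 says that "plasma cell clonal responses against conserved epitopes may be smaller in number and less prone to persist". If this means fewer cells per clone, cross-reactive clones would drop below detection sooner than strain-specific ones even at equal true maintenance, and the test could report a difference that is not there.

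**Working it through.** **1. The plan's own figure.** Inputs from Section 11.2: difference 33 - 11 = 22 points, SD 44, so δ/σ = 0.5; power 80%; P < 0.05. With the 33% treated as known and a one-sided test, n = (1.645 + 0.842)² / 0.5² = 6.18 / 0.25 = 24.7, so 25. This is the stated number. As a two-sided 1:1 comparison, n = 2 × (1.960 + 0.842)² / 0.25 = 62.8, so 63 per group. That gap is a separate matter and does not depend on how undetectable clones are scored.

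**2. What the documents imply for a non-detect.** The variable is r = f(365) / f(28). In sequencing data a clone with no reads has f(365) = 0, so r = 0%, a value the t-test accepts. Section 11.2 treats undetectable clones as evidence of low maintenance, so they count as data. Dropping them would contradict that reading.

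**3. The extreme case.** Suppose all 25 cross-reactive clones are undetectable and all receive one value v. Take 25 comparator clones (assumed) with mean 33 and SD 44. The pooled SD is √(24 × 44² / 48) = 31.1, the standard error is 31.1 × √(2/25) = 8.8, and t = (33 - v) / 8.8 on 48 degrees of freedom.

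| v | t | two-sided p |
|---|---|---|
| 0% | 3.75 | 0.0005 |
| 5% | 3.18 | 0.003 |
| 10% | 2.61 | 0.012 |
| 15% | 2.05 | 0.046 |
| 20% | 1.48 | 0.146 |

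A clone at 10 times the limit on Day 28 has an upper bound of 1/10 = 10%; at 100 times it is 1%. The conclusion is therefore the same at 0 and at the bound until the bound passes about 15%, that is, until clones were already within about 1/0.15 = 6.7 times the limit on Day 28. If all 25 were dropped, no test would be possible.

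**4. Power by scoring rule.** Simulation with 1,000 runs per cell, 25 cross-reactive and 100 strain-specific clones, lognormal maintenance, equal clone size and true means of 11% and 33%. The clone count of 100, the distribution and the clone sizes are assumed. Cells show power at a median Day 28 size of 10x / 30x / 100x the limit.

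| Setting | Scored 0 | At the limit | Dropped |
|---|---|---|---|
| Cross-reactive SD 14.7% (same CV) | 83 / 88 / 89% | 61 / 85 / 88% | 24 / 61 / 83% |
| SD 44% in both groups | 76 / 80 / 81% | 54 / 75 / 79% | 7 / 20 / 52% |
| Same CV, assay error of log-SD 0.5 | 58 / 60 / 60% | 35 / 53 / 59% | 7 / 27 / 48% |

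At 5x the limit, scoring 0 gives 76% (same CV, no error). A second simulation used gamma-distributed maintenance, 25 clones per group and a fixed limit of 10% of the Day 28 frequency. It gave 74% scored 0, 71% at the limit and 27% dropped. With the limit at 1%, scoring 0 and scoring at the limit both gave 74%. The large loss comes from dropping. Choosing between 0 and the limit matters mainly when clones are already close to the limit at Day 28.

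**5. False positives at equal true maintenance, no assay error, 5x to 100x.**

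| Cross-reactive clone size | Scored 0 | Dropped | At the limit |
|---|---|---|---|
| Equal | 5-6% | 5-6% | 4-6% |
| 3-fold smaller | 5-10% | 6-17% | 5-33% |
| 10-fold smaller | 7-23% | 15-41% | 9-83% |

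Scoring 0, the rule the documents imply, is the least distorted in the two lower rows. Nothing in the documents supports a 10-fold size difference.

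**6. Would a censored (Tobit) model on log(Day 365 / Day 28) do better?** Under lognormal maintenance its power was 99-100% against 84-88% for the t-test scored 0. Under gamma maintenance it was 88 / 81 / 82% against 85 / 84 / 90% at 10x / 30x / 100x. With 40% of clones truly lost, at 100x, it was 26% against 45% (lognormal) and 26% against 37% (gamma). Its false positives under true loss reached 10% with cross-reactive clones 3-fold smaller and 14% with them 10-fold smaller. If every cross-reactive clone is undetectable, as in the preliminary data, it has no finite estimate.

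**The case for a change.** The strongest reply is that an implied rule is not a written one. Section 11.4 leaves an analyst free to drop non-detects or substitute a limit after seeing the data, and the tables show that dropping is damaging: power can fall from 83% to 24%, and with SD 44% in both groups and gamma maintenance the observed difference even reverses sign. Section 8.2 also names two assays, and the decay-constant analysis in Section 11.4 cannot take the logarithm of a zero.

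Part of this stands. The rule is unwritten, the detection limit is unstated, and if cross-reactive clones were much smaller at Day 28 even scoring 0 would inflate false positives. The rest is weaker. Dropping is the option that Section 11.2's own interpretation argues against. Section 3.2.3 and the source of the 33% settle the assay as sequencing. The phrase about conserved-epitope responses can equally mean fewer clones, which causes no such bias. The decay model is described as still to be developed, so its treatment of zeros belongs to that work. Assay conventions may also sit in the Data Management Plan cited in Section 11.4 or the Manual of Procedures mentioned in Section 14.6, neither of which is available here.

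**Conclusion.** No change to the plan follows. The text leaves a gap, but Sections 3.2.3 and 11.2 together lead a sensible analyst to one treatment: keep undetectable clones in both groups at 0% and run the planned t-test. Under that treatment power is 83-89% (same CV) or 76-81% (SD 44% in both groups) at 10x to 100x the limit, and false positives stay at 5-10% up to a 3-fold difference in clone size. The lower power with assay error (58-60% scored 0) reflects measurement noise, and neither of the other scoring rules recovers it.

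A censored model would be a debatable supplement, since its advantage depends on the assumed distribution and it fails in the very case the preliminary data show. The comparison concerns an exploratory measure; the primary outcomes in Section 3.2.1 (antibody-secreting cells, memory B cells and HAI titres) are unaffected.

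These figures rest on assumed clone sizes, comparator counts, distributions and detection limits. The conclusion would weaken if cross-reactive clones proved to be many times smaller than strain-specific ones at Day 28, which the documents do not establish.

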needed to secure the appropriate approvals and clearance to bring research participants back for their missed visits. As such, we would like to request that the missed visit windows for the Day 28 and Day 90 visits be extended for a maximum of up to 180 days, to ensure that ample time is available to bring participants back for their missed visits. Enrollment for this study ended on March 31, 2020.

Subjects will be offered the opportunity to participate in the study for up to 3 consecutive years provided eligibility criteria is met each year. Subjects who elect to continue in the study after first year of participation will be rescreened to verify continued eligibility and re-consented prior to subsequent participation. Re-enrolling subjects will receive new subject identifiers and will count towards the total enrollment number for subsequent years of participation. A separate subject record will be maintained each year a subject re-enrolls in the study.

Schematic of Study Design:

| Subjects enrolled in study | Years study performed | Number of subjects per year (study total) | Blood or Bone Marrow samples (days post-influenza vaccination) |
|------------------------------|-----------------------|--|---|
| Healthy adults (18-49 years) | Years 1-4 | Years 1-3: 15/year Year 4: 10 (Total: 55) | Blood volume 64ml per visit (320 ml total)– Day: 0, 7, 14, 28, 90, 365* Bone marrow aspirate volume 30 ml per visit (90ml total)– Day: 0, 28, 365* |

* Subjects that consent to be in the study for subsequent years, the “Day 0” of the second and third years will constitute “day 365” and “day 730” with respect to the first year of participation.

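### Section 11.4 plans marrow decay constants for each clone and decline phase, but two post-vaccination marrow samples yield one net rate, and none for a clone undetectable at one year

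*Combined protocol and SAP*

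**What the plan says.** Section 11.4 has three parts. First, a test of one-year marrow frequency as a percentage of one-month frequency: "We will use the unpaired Student's t-test to compare the frequencies of strain-specific and broadly cross-reactive clonotypes". Second, a multi-phase exponential decay model for blood and bone marrow. Third, an ANOVA of specificity, affinity and hypermutation on the "decay constants of individual clones in each decline phase that we identify through our modeling".

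The marrow data for this are set out in section 3.2.3: "Use deep sequencing to track the frequency of each clonotype in the bone marrow plasma cell compartment at days 0, 28, and 365 post-vaccination". Appendix A gives the same aspirate days. Subjects may re-enrol, and the footnote to the design schematic in the Protocol Summary says that the Day 0 visits "of the second and third years will constitute" day 365 and day 730 of the first year. Appendix A shows that re-enrolling subjects are vaccinated again at Day 365, and section 3.2.3 asks the study to "examine whether the same plasmablast clones are re-amplified after each vaccination".

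Section 11.2 gives average one-year maintenance as about 33% of the one-month frequency (SD 44%). The few cross-reactive clones tracked so far were "undetectable after one year, suggesting that their maintenance is substantially lower than the average clone". Section 8.2 measures clone frequency by both sequencing and quantitative PCR. The protocol gives no detection limit, does not say which assay decides detectability, and has no scoring rule for an undetectable clone.

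**The concern.** A decay constant in each phase needs enough time points to separate the phases. The Day 0 aspirate precedes the vaccine, so it is not on the decay curve of a vaccine-induced clone. That leaves two marrow points per vaccination. Any marrow phase constants fed to the ANOVA would reflect the assumed curve, and a finding that specificity or hypermutation acts on the slow phase could not be checked against the data.

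Even a single net rate is a log ratio, and it has no value when the one-year frequency is zero. That is the only one-year outcome the plan reports for the cross-reactive clones, the class of most interest. Without a rule fixed beforehand, the scoring could be chosen after the data are seen.

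**Working it through.** **The plan's own figures.** Section 11.2 wants 25 cross-reactive clones to detect 11% v 33% with SD 44% and 80% power at P<0.05. (1.645 + 0.842)² × (44/22)² = 24.7, so 25 reproduces as a one-sided test against a comparator mean taken as known. Sidedness is not stated; that is a separate matter. Then 25/0.5 = 50 donors, and 55 × 0.9 = 49.5. This comparison therefore sets the sample size.

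**Step 1: what two marrow samples determine.** Elapsed time is 365 − 28 = 337 days. The net rate is k = ln(F28/F365)/337.
- 33% maintenance: k = 1.109/337 = 0.0033 per day, half-life 0.693/0.0033 = 211 days.
- 11% maintenance: k = 0.0065 per day, half-life 106 days.

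A two-phase curve has four parameters (three if scaled to day 28). At days 28 and 365 its Jacobian has rank 2. Solving f·exp(−337a) + (1−f)·exp(−337b) = 0.33 for the slow rate b, with illustrative fast phases:

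| Fast share f | Fast half-life | Slow half-life |
|---|---|---|
| none | none | 211 days (single phase) |
| 30% | 30 days | 310 days |
| 60% | 45 days | 1153 days |

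Check of the last row: the fast part leaves 0.6 × 0.5^(337/45) = 0.003, so the slow part keeps (0.33 − 0.003)/0.4 = 0.817, and 337 × 0.693/−ln(0.817) ≈ 1153 days. All three curves pass exactly through both samples, and the slow (or only) half-life spans more than 5-fold (1153/211 = 5.5).

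**Step 2: a clone undetectable at one year.** With F365 = 0, k is infinite. If a limit is substituted, the limit determines k. For assumed limits of 10%, 5%, 1% and 0.1% of the day-28 frequency, k = 0.0068, 0.0089, 0.0137 and 0.0205 per day, a 3-fold range.

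**Step 3: does this spoil the t-test on percentages?** It can run with 0% entered. Scoring affects power: if all 25 cross-reactive clones are undetectable, against an assumed 25 strain-specific clones with SD 44%, two-sided power is 74% scored at 0, 60% at 5% and 44% at 10%.

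For false positives, simulate equal true persistence in both classes (mean 33%, SD 44%), 25 cross-reactive v 25 to 100 strain-specific clones. Assume that strain-specific clones start at 20 times the limit and cross-reactive clones at the multiple shown. With a lognormal shape (μ = −1.619, σ = 1.011; 20,000 runs), rejection at a nominal 5% is:

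| Cross-reactive start | Scored 0 | Half limit | Full limit |
|---|---|---|---|
| 10x | 4–5% | 4–5% | 4–5% |
| 5x | 8–9% | 4–5% | 8–9% |
| 3x | 17–23% | 4–5% | 32–33% |
| 2x | 31–42% | 9–10% | 73–81% |

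Scoring 0 lowers the cross-reactive mean (18% at 2x) and scoring the full limit raises it (59% at 2x). If both classes start equally near the limit, scoring 0 rejects 4–5%.

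Now change only the shape: 60% of clones lost and 40% retained at a mean of 82.5%, which has the same 33% mean and 44% SD. The zero-scored t-test then rejects 4–6% at every multiple from 10x to 2x. A left-censored log-rate regression, which holds about 5% under the lognormal, rejects about 16–20% at 5x to 2x (separate sets of runs ranged from 12% to 28%).

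**Step 4: visit timing.** Day 365 has a window of three months either way. With constant decay to one third, k = ln(3)/337 = 0.00326 per day, and the percentage reads 45% at Day 275 and 25% at Day 455. This is noise rather than bias between classes, but it is a reason to divide by actual days.

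**The case against.** The strongest reply is that section 11.4 only undertakes to work towards a model and uses whichever phases the modelling identifies. If marrow shows one phase, one constant results. That is fair as to intent, but with two points per clone the data cannot identify a second marrow phase, so the text should say that one is meant.

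Other sources of information do not fill the gap. Blood is drawn at five post-vaccination times, which is why its modelling can stand, but section 3.2.3 tracks clones there mainly as memory B cells and section 2.1 calls the blood ASC response short-lived. Re-enrolled subjects give later marrow samples, but after another vaccine dose. Pooling over the spread of Day 365 visit dates might inform a population curve under strong assumptions, but not constants of individual clones.

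A reader might infer that the t-test is biased against cross-reactive clones. The documents do not support that. They give no starting frequencies. The remark in section 11.2 that "plasma cell clonal responses against conserved epitopes may be smaller in number and less prone to persist" may mean fewer clones rather than rarer ones, and section 8.2 selects clones found in several wells of Day 7 blood. A detection rule may also sit in the Manual of Procedures mentioned in section 14.6.

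A reader might also want a censored regression in place of the t-test. Step 3 argues against it: sections 2.1 and 3.2.3 describe clones as persisting or being lost, and under that shape the regression is the method that loses control of its error rate.

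Finally, the t-test has no person term, although "Re-enrolling subjects will receive new subject identifiers and will count towards the total enrollment number". In simulation (assumed 40 persons, 55 enrolments) ignoring the person was slightly conservative: 2.0–4.3% rejection at within-person correlation 0.2–0.5, against 4.4–4.8% with none. Section 11 already names mixed models. This is minor.

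**Conclusion.** The marrow part of the planned ANOVA cannot be carried out as written. Each clone supplies one net marrow rate per vaccination, and that conclusion rests only on the sampling schedule and on not assuming that revaccinated clones stay on their first curve. The half-life splits are illustrations of how wide the ambiguity is, not estimates.

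The missing rule for undetectable clones is a real gap for that rate, which has no value at zero. For the t-test it is unstated detail. Bias there needs cross-reactive clones starting at about 2–3 times the limit with strain-specific clones well above it, and also depends on the shape of the distribution; all of these are assumptions.

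The reach is limited. Section 3.2.3 lists clonotype tracking as exploratory, and the primary outcomes in section 3.2.1 are unaffected. It still deserves correction because section 11.2 sizes the study on this clone comparison and calls plasma cell longevity a major goal.

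**What to change.** For marrow, delete the words *in each decline phase* in section 11.4 and write:

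> Each clone contributes one net marrow rate per vaccination, log(one-month/one-year frequency) divided by actual elapsed days; specificity, affinity and hypermutation will be analysed on this rate. A clone undetectable at one year has a rate known only to be at least the value at that sample's detection limit; the analysis will be run with such clones at the limit and at half the limit, and a conclusion drawn only if both agree.

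Leave the blood modelling as written. Keep the planned t-test on percentages, state that undetectable clones are scored 0, and add sensitivity analyses at half the limit and at the full limit. Report counts of detected and undetected clones by class, and name the assay that decides. A left-censored regression may be added as a further sensitivity analysis but should not replace the t-test.

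The cost is the loss of the marrow-phase claim, a detection limit to be derived for each sample, and a few extra analyses; no new visit or sample is needed. The two scoring values do not bracket the true rate, which has no upper bound when a clone is undetectable, so agreement between them is a check and not proof.
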